### **9.2.1 Per-protocol Population**

For the primary endpoint, participants must have completed the pre and post-CARE assessment to be included in the per-protocol (PP) population.

For the exploratory endpoint, participants must have completed the post-CARE assessment, to be included in the per-protocol (PP) population.

## **9.3 Analysis Plan**

Summary statistics of the schools and staff in the three cohorts (teacher, staff administrative and staff non-administrative) will be presented using data collected during pre- and post-CARE assessment. We will not share data categorized by role with school districts. We will only share aggregate data grouped by schools with school districts if there are more than 10 participants. If there are fewer than 10 participants at a school, we will group schools together to provide a summary report. If the number of workshop participants for the administrative or non-administrative staff group is less than 10, then these participants will be grouped together and identified as “staff.” Under these circumstances, there will be two cohorts instead of three. Means/medians with standard deviations (and interquartile ranges) will be tabulated.

Descriptive statistics (i.e. number of observations, mean, standard deviation, median and interquartile range) will be presented for continuous variables (e.g. as age, weight, etc.). Other descriptive statistics such as counts, proportions, and/or percentages will be presented to summarize discrete variables (such as race, sex, etc.). All descriptive analyses will be presented by appropriate stratification group and overall as specified under each analysis section.

The analysis and PP populations will be used for the primary and exploratory analyses, unless otherwise specified. A detailed description of statistical methods for all analyses will be prepared and presented in the statistical analysis plan prior to data lock for final analyses.

### **9.3.1 Primary Analysis**

For the first primary endpoint for the teacher, staff administrative and staff non-administrative cohorts (change in CARE assessment scores after professional development intervention compared to before), the overall proportions will be reported and the change from pre- to post- will be presented in graphical form (bar chart).

95% confidence intervals for raw change in pre-post assessment scores for each assessment will be computed using a non-parametric bootstrap.

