### **2.1.1 Background of Professional Development Workshop and Evaluation**

In addition to the direct pandemic-mediated impact on children, teachers' attitudes can impact their students' mental health. We also suspect school staff may play a role in students' mental health. Thus, Cultivating Awareness and Resilience in Education (CARE) has been proposed as a potential professional development workshop to help improve teachers' and staff's mental health, well-being, effectiveness and student wellness. CARE provides teachers and staff with tools and resources to reduce stress, prevent burnout, enliven teaching, and help students thrive socially, emotionally, and academically. The program will be presented in one to four face-to-face training sessions, spread out over one to four months, and provides post-training resources as additional support. CARE blends instruction with experiential activities, reflection, and discussion. Tools used by the program include mindful awareness practices, emotion, and caring skills training to support more equitable and caring classrooms. Research showed CARE workshops help improve emotional awareness, self-regulation, well-being, cardiovascular health, efficacies, mindfulness, and burnout/time-related stress. Improving teachers' ability to handle their own stress allows them to provide better emotional support to their students and may also help reduce schools' teacher attrition.

As part of this study, people who participate in CARE will be asked to answer questionnaires about demographic information, mental health, well-being, classroom instruction, and behavior management prior to the workshop and two times after completing the workshop. The ABC Science Collaborative is providing this professional development workshop as a service that participating schools offer to all teachers and staff. Those that want to participate in pre- and post-intervention assessments will be consented prior to doing so. Participation in the intervention and assessment completion is optional.

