## 4.2 Scientific Rationale for Study Design

School employees will participate in the intervention for up to 1 year. The pre-intervention CARE assessment battery for teachers and staff will be distributed for completion up to one month prior to the CARE teacher and staff resiliency workshop. The post-intervention CARE assessment battery will be distributed for completion at one-week post intervention and two months post-intervention.

Based on clinical experience of the investigators and published data, the one-week post intervention time point provides insight into the immediate uptake of skills and improvement in emotional well-being of participants who have completed a resiliency workshop. The two-month post-intervention time frame aids in the determination of which skills and concepts endured over time.

The resiliency workshop is delivered across one to four days during a one to four-month period to provide teachers and staff the opportunity to practice skills they have learned prior to being introduced to new concepts and techniques. The CARE team follows up with participants via email on a weekly basis to provide reminders of prior practices and context for their use. This approach has been shown to be effective for promoting teacher and staff mental health and well-being in prior iterations of this workshop. Staff will be identified as either non-administrative staff or administrative staff. Non-administrative staff and teachers attend CARE workshops together and do not include administrative staff to promote openness and feedback.

Administrative staff attend CARE workshops that are designed to meet the unique needs of principals and administrators. Specifically, at least six studies have investigated effectiveness of CARE on improving classroom learning, general participant well-being, self-efficacy, reduced burnout, improved self-awareness, self-care and compassion, and mindfulness. Additional work has demonstrated the impact of CARE on teachers' cardiovascular health, including lower heart rate.

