## 6.3 Intervention

The intervention will be a professional development workshop for teachers and staff delivered across one to four days. The CARE intervention aims to help teachers and staff handle the stresses of school-related work by offering tools and resources for reducing stress, preventing burnout, enlivening teaching, and helping students thrive socially, emotionally, and academically. Tools include mindful awareness practices and caring and emotion skills training. Each intervention workshop includes 30 to 35 participants and a facilitator, who is part of the CARE team. The workshops will be held at a location selected by the school, likely on their campus.

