## 6.5 Evaluation Details

### 6.5.1 Summary of Evaluations

Applicable informed consent will be documented for all participants. Participants will be asked to complete the pre-intervention CARE assessments online at the time of consent (up to one month before the intervention). The post-intervention CARE assessments will be completed online by participants one week after and two months after the intervention. REDCap will be used to distribute electronic consents and the pre- and post-assessments using a public link sent to the school administrator(s), who will then distribute it to the participating teachers and staff. Participants' email addresses will be collected within the REDCap survey and will be used solely for payment/incentive purposes. No additional assessments will be collected from the participants as part of this study.

Participants will be instructed that all questions are optional. The questionnaire will include the following:

- Demographic variables
- CARE Assessments

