### 6.5.2 Demographic Variables

Participants will be asked a series of questions about their demographics, including their race, ethnicity, gender, school name, school role (administrative staff, non-administrative staff or teacher), and the total number of years they have taught, at current grade level and at current school. We will not share data categorized by role with school districts. We will only share aggregate data grouped by schools with school districts if there are more than 10 participants. If there are fewer than 10 participants at a school, we will group schools together to provide a summary report. If the number of workshop participants for the administrative or non-administrative staff group is less than 10, then these participants will be grouped together and identified as "staff."

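### The primary 95% bootstrap intervals name no resampling unit and make no allowance for clustering by workshop or school, so they may be too narrow

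*Combined protocol and SAP*

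**What the plan says.** The inferential part of Section 9.3.1 is one sentence: "95% confidence intervals for raw change in pre-post assessment scores for each assessment will be computed using a non-parametric bootstrap". It gives no resampling unit, interval type or number of resamples. Section 9 does not mention clustering, correlation or an ICC, and Section 9.4 reports no formal sample size calculation. Section 9.3 adds that "A detailed description of statistical methods for all analyses will be prepared and presented in the statistical analysis plan prior to data lock"; the supplied document contains no later text that settles the resampling unit.

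Delivery is in groups. Section 6.3 states that "Each intervention workshop includes 30 to 35 participants and a facilitator", at a location chosen by the school. Section 2.1.1 (the workshop background) says that "The program will be presented in one to four face-to-face training sessions, spread out over one to four months". Section 4.2 says that "Non-administrative staff and teachers attend CARE workshops together and do not include administrative staff", while Section 9.1.1 analyses teachers, non-administrative staff and administrative staff as three separate cohorts.

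On identifiers, Section 6.5.2 lists "school name, school role (administrative staff, non-administrative staff or teacher" among the items collected, but no workshop identifier. Section 6.5.1 adds that "Participants will be instructed that all questions are optional".

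**The concern.** A non-parametric bootstrap with no further description is normally read as drawing participants one at a time with replacement, which treats their changes as independent. People in one workshop share a facilitator, a group, a schedule and often a school. Where these differ between workshops, changes can be correlated within a workshop.

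Taking each person's change score removes stable differences in level between schools, so only correlation in the change itself matters. If that correlation is positive, participant resampling misses the between-workshop part of the variance.

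The plan has no hypothesis test or decision rule, so no error rate for a decision is at stake. What is at stake is the stated precision of the main reported result: intervals labelled 95% would cover less than 95% and make the average change look better determined than it is. Point estimates are not affected.

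**Working it through.** The plan states no ICC, standard deviation, interval width or power, so there is no figure of its own to reproduce. The check asks how far coverage falls over a range of assumptions.

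**Inputs**
- Confidence level 95%, so z = 1.96 (Section 9.3.1).
- Workshop size 30 to 35, midpoint 32.5 (Section 6.3). This is the upper case for m, the number analysed per workshop within one cohort.
- Smaller m of 5, 10 and 20: assumed. They are plausible because two cohorts share workshops (Sections 4.2 and 9.1.1) and assessment is optional (Sections 2.1.1 and 6.5.1).
- ICC of change from 0 to 0.10: assumed.

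**Formulas**
- Design effect: DE = 1 + (m − 1) × ICC.
- Factor by which a correct interval is wider: √DE.
- Actual coverage of a participant-level 95% interval: 2Φ(1.96/√DE) − 1.

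**Examples at ICC 0.05**
- m = 10: DE = 1 + 9 × 0.05 = 1.45; √DE = 1.20; coverage 89.6%.
- m = 32.5: DE = 1 + 31.5 × 0.05 = 2.575; √DE = 1.60; coverage 77.8%.

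**Coverage (width factor)**

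| m | ICC 0.01 | ICC 0.02 | ICC 0.05 | ICC 0.10 |
|---|---|---|---|---|
| 5 | 94.5% (1.02) | 94.1% (1.04) | 92.6% (1.10) | 90.2% (1.18) |
| 10 | 94.0% (1.04) | 92.9% (1.09) | 89.6% (1.20) | 84.5% (1.38) |
| 20 | 92.8% (1.09) | 90.5% (1.17) | 84.0% (1.40) | 75.0% (1.70) |
| 32.5 | 91.3% (1.15) | 87.5% (1.28) | 77.8% (1.60) | 66.4% (2.04) |

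At ICC 0, DE = 1 and coverage is 95% for every m.

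**Simulation check** (2,000 data sets, 500 resamples, normal changes, equal cluster sizes; percentile intervals assumed because the plan names no type)

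| Setting | Method | ICC 0 | 0.01 | 0.02 | 0.05 | 0.10 |
|---|---|---|---|---|---|---|
| 30 clusters of 10 | Participant bootstrap | 93.6% | 93.2% | 91.2% | 89.4% | 84.6% |
| 30 clusters of 20 | Participant bootstrap | 94.8% | 92.4% | 89.5% | 83.7% | 74.7% |

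These agree with the formula to within about two percentage points.

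**Alternatives, over the same ICC range**
- 30 clusters of 10: resampling whole clusters covered 92.2% to 93.6%; a t interval on cluster means covered 94.0% to 95.2%.
- 6 clusters of 10 (an assumed illustration of a small cohort): the cluster bootstrap covered only 84.6% to 87.4%; the cluster-level t interval covered 94.6% to 96.0%.

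**Number of clusters.** The maximum of 1,000 participants (Section 9.4) would fill 1,000/35 = 28.6 to 1,000/30 = 33.3 workshops if everyone attending enrolled. A single cohort, most likely the administrators, may have far fewer.

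**The case against.** The strongest reply is that this is an unspecified detail, not a stated error. Section 9.3 promises full methods before data lock, the resampling unit is the sort of detail such a plan supplies, and a cluster bootstrap is also non-parametric. That is fair as far as it goes: the point can be settled without contradicting Section 9.3.1. But the supplied text does not settle it. A plan written just before data lock also cannot recover a workshop identifier that was never recorded.

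Second, the ICC is assumed. The documents do not say that facilitators differ between workshops, or that the number of sessions varies from one workshop to another. This stands. The documents cannot separate no problem from a serious one, and the figures above are illustrations over a range.

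Third, 30 to 35 describes attendance, not the number analysed in a cohort. This also stands. Sections 6.5.2 and 9.3 even provide for staff groups of fewer than 10. At m = 5 the loss is small up to ICC 0.02, and coverage is still 90.2% at ICC 0.10.

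Fourth, a cluster bootstrap can do worse than the method it replaces. A separate simulation with 6 clusters of 10 gave 85.8% to 86.4% for the cluster bootstrap at ICC 0 to 0.05, against 93.1% falling to 88.2% for the participant bootstrap; the cluster bootstrap was better only at ICC 0.10 (85.4% against 82.7%). This is correct, and is why the fix needs a small-sample method.

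Finally, participant resampling is defensible if the target is only the average change in the workshops actually delivered. That is so, but the plan states no such target, and its primary objective speaks of K-12 teachers and staff in general.

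**Conclusion.** The concern holds, in conditional form. The plan gives neither a resampling unit nor an allowance for clustering, and its usual reading yields intervals that are too narrow whenever change is positively correlated within workshops or schools.

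The size cannot be fixed from the documents. It runs from nothing at ICC 0, through intervals that should be 1.20 times wider at ICC 0.05 with 10 analysed per workshop, to 2.04 times wider at ICC 0.10 with a full workshop of 32.5 in one cohort. The conclusion assumes that participants would be resampled singly and that the interval is meant to describe the program beyond the workshops delivered. It should be fixed, because the interval is the primary endpoint's only measure of uncertainty. Confidence in its practical importance is moderate, because the ICC is unknown.

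**What to change.** In Section 9.3.1, or in the detailed analysis plan promised in Section 9.3:

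1. State what the interval is for: the workshops delivered, or the program more broadly.
2. If it is the program, state that whole clusters are resampled (workshop, or school where workshops sit within schools) and that each person's pre and post scores stay together.
3. For a cohort with few clusters, use a t interval on cluster means or a mixed model with a random cluster effect and small-sample degrees of freedom. Set the cut-off for few clusters before the data are seen, or use the small-sample method in every cohort. If cluster sizes are very unequal, say whether the mean is taken over people or over clusters.
4. Add a workshop identifier in REDCap while data are being collected. Because answers are optional, a self-reported identifier or school name may be incomplete; a separate survey link for each workshop would avoid relying on the answer.
5. Report the ICC of change for each assessment.

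The cost is a few sentences and one data field. The intervals will be wider, possibly very wide for the administrative cohort.

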## **9.4 Sample Size Considerations**

No formal sample size calculation was completed for this study. This study will enroll as many adults as possible during the study period, up to 1,000 total participants.

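### The 95% bootstrap intervals name no variant and can be applied to staff cohorts of 10 or fewer, where the usual variants would cover about 84% to 90%

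*Combined protocol and SAP*

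**What the plan says.** The primary endpoint in section 9.1.1 is the change in raw score on five instruments, listed separately for teachers, non-administrative staff and administrative staff. The only inferential statement in section 9.3.1 is that "95% confidence intervals for raw change in pre-post assessment scores for each assessment will be computed using a non-parametric bootstrap". It gives no variant, number of resamples, resampling unit or minimum number of participants, and does not say whether the interval is for a mean or a median.

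Section 9.3 has one rule about small groups: "If the number of workshop participants for the administrative or non-administrative staff group is less than 10, then these participants will be grouped together". It continues: "Under these circumstances, there will be two cohorts instead of three". The rule therefore sets the analysis cohorts as well as the reports to school districts. It counts workshop participants. Section 9.2.1 says that for the primary endpoint "participants must have completed the pre and post-CARE assessment to be included in the per-protocol (PP) population", and section 6.5.1 adds: "Participants will be instructed that all questions are optional".

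Section 9.4 states: "No formal sample size calculation was completed for this study". Enrolment is "up to 1,000 total participants", with no split by cohort. On methods, section 9.3 says: "A detailed description of statistical methods for all analyses will be prepared and presented in the statistical analysis plan prior to data lock".

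**The concern.** The familiar bootstrap intervals for a mean (percentile, basic, BCa) take their spread from the observed sample. They correct neither for the n versus n−1 divisor nor for the uncertainty in the estimated standard deviation that the t distribution allows for. With hundreds of pairs this does not matter. With about 10 it makes the interval too short for its 95% label.

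The plan permits a separate staff cohort at 10 workshop participants. Assessments and individual questions are optional, and a change score needs both a pre and a post value, so a cohort that just passes the rule can have fewer than 10 usable pairs on a given instrument at a given follow-up. If one of the usual variants is then used, the intervals for that cohort would exclude the true change more often than the stated 5%. These intervals are the only measure of uncertainty in the primary analysis.

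**Working it through.** **Inputs.** From the documents: nominal level 95% (9.3.1); smallest separate staff cohort 10 workshop participants (9.3); change needs both assessments (9.2.1). The documents give no standard deviation, shape of the change scores or retention rate, so those below are assumptions. They also state no achieved coverage, so the only figure to compare with is the nominal 95%.

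**Step 1: closed form, normal changes, percentile interval for a mean.** The half-width is about 1.96 × s × √((n−1)/n) / √n. Coverage is therefore

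2 × T(n−1)[1.96 × √((n−1)/n)] − 1,

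where T(n−1) is the t distribution function on n−1 degrees of freedom. At n = 10 the argument is 1.96 × √0.9 = 1.859 on 9 degrees of freedom, which gives 90.4%.

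| Usable pairs | 5 | 7 | 8 | 10 | 15 | 20 | 30 | 50 | 100 |
|---|---|---|---|---|---|---|---|---|---|
| Coverage, % | 84.6 | 88.0 | 89.1 | 90.4 | 92.1 | 92.9 | 93.6 | 94.2 | 94.6 |

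If 10 workshop participants yielded pairs at an assumed 80%, 70% or 50%, the entries that apply are those for 8, 7 and 5 pairs.

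**Step 2: simulation at 10 pairs.** There were 6,000 simulated cohorts with 1,000 resamples each, and the Monte Carlo standard error is about 0.4 points. The target is the mean change and participants are independent. Coverage in %:

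| Change distribution (assumed) | Percentile | Basic | BCa | Bootstrap-t | Paired-t |
|---|---|---|---|---|---|
| Normal | 90.1 | 90.1 | 90.0 | 95.0 | 95.0 |
| Rounded normal | 90.5 | 90.6 | 90.1 | 94.4 | 95.1 |
| Gamma, shape 2 | 87.9 | 86.6 | 88.6 | 94.5 | 92.4 |
| Exponential | 85.9 | 83.6 | 87.3 | 93.8 | 89.6 |
| Half zeros, rest rounded normal | 88.5 | 86.7 | 89.2 | 90.8 | 92.0 |
| t with 3 df | 89.3 | 92.0 | 86.4 | 92.8 | 96.0 |

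The first three columns lie near 90% for the two normal cases and between 83.6% and 89.2% for the two skewed cases and the zero-inflated case. BCa does not repair the shortfall. Bootstrap-t and paired-t each equal or exceed all three in every row.

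**Step 3: larger cells.** At 30 pairs (3,000 simulated cohorts) the three usual variants cover 93.1% to 93.3% for normal changes, 91.6% to 92.6% for gamma, 90.9% to 92.2% for exponential and 92.9% to 93.5% for zero-inflated changes. Bootstrap-t covers 94.5% to 95.1% in these four cases.

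**Step 4: width.** The percentile half-width divided by the paired-t half-width is 1.96 × √((n−1)/n) / t(0.975, n−1):

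- n = 7: 1.815 / 2.447 = 0.74, so the paired-t interval is 1/0.74 = 1.35 times as wide.
- n = 10: 1.859 / 2.262 = 0.82, or 1.22 times.
- n = 20: 1.910 / 2.093 = 0.91, or 1.10 times.

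**Step 5: error rate.** For normal changes the percentile non-coverage relative to 5% is 9.6/5 = 1.9 times at 10 pairs and 6.4/5 = 1.3 times at 30. The worst cell of the step 2 table gives 16.4/5 = 3.3 times.

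**The case against.** **The plan does not choose an interval that under-covers.** This stands. A reader might infer that any non-parametric bootstrap fails at 10, but section 9.3.1 names no variant and the studentized bootstrap covers 93.8% to 95.0% in four of the six settings tried (90.8% and 92.8% in the others). Section 9.3 also leaves the detail to an SAP due before data lock, so the gap can still be closed there. What remains is that the text equally permits the three variants that fall short, and nothing in it asks for a small-sample correction.

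**Ten is a floor, not an expected size.** This also stands. Section 6.3 puts 30 to 35 people in each workshop and section 4.2 gives administrators their own, so one full administrative workshop would start at about 30. The teacher cohort is likely to be large. The documents do not support saying that a cohort near 10 will occur. They support only that the plan allows one, with no allowance for optional completion.

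**The cut-off of 10 is a privacy rule.** Partly right. The same wording appears in sections 6.5.2 and 13.3 in the context of sharing data with districts. Section 9.3 nevertheless makes it decide whether there are two or three analysis cohorts.

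**The paired-t interval is not a full remedy.** Right. At 10 pairs it covers 92.4%, 89.6% and 92.0% under gamma, exponential and zero-inflated changes. It improves on the usual bootstrap variants without always reaching 95%.

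**Little depends on these intervals.** A reader might infer that false findings in staff cohorts would triple. That is the worst assumed case, and under normal changes at 10 pairs the factor is 1.9. The plan attaches no test, success criterion or decision to the intervals.

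**Conclusion.** The point holds conditionally. If 9.3.1 is carried out with a percentile, basic or BCa interval for the mean change, a staff cohort with 10 usable pairs gets about 90% coverage for roughly normal changes and about 84% to 89% for most skewed or zero-inflated changes. With 7 pairs coverage is about 88% for normal changes. For normal changes the shortfall is minor at 30 pairs and negligible at 100. With skew it is still 2 to 4 points at 30.

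The result rests on three assumptions: the target is a mean, the change distributions are ones the documents do not specify, and participants are independent. Clustering by workshop or school was left out; positive correlation within workshops would lower coverage further, and the fix below does not address it. How far the point matters depends on whether a small staff cohort arises, which the documents do not settle. It is a cheap improvement to an incomplete specification, not an error that undermines the primary analysis.

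**What to change.** In section 9.3.1, or in the SAP before data are examined:

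1. State that the interval is for the mean change and use the studentized (bootstrap-t) interval throughout. Alternatively, use the paired-t interval in any cohort, instrument and time-point cell with fewer than about 30 usable pairs. The first option keeps one method across the display. The second is simpler to run and did better at 10 pairs with many zero changes. The figure of 30 is a convention that matches where the shortfall becomes minor for normal changes.
2. Apply the merging rule in section 9.3 to participants with a usable pre-post pair instead of workshop participants. Say whether the count is made once per cohort or for each instrument and time point; once is simpler, because the cohorts then stay the same in every display. The district-sharing rule can stay as it is.

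Dropping intervals altogether below 10 pairs is optional and does not follow from the coverage results.

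**Cost:** a few sentences and no new data. In small cohorts the paired-t interval is about 10% (20 pairs) to 35% (7 pairs) wider than the percentile interval. The width of the bootstrap-t interval was not computed, but its higher coverage also has to be paid for in width. Counting pairs may merge the two staff groups more often, which loses the separate administrative result in those cases.
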